2.2 Clinical Study Objectives

Effectiveness

Confirm the effectiveness of BBL injection for the correction of volume loss in the IOH area by demonstrating superiority to untreated control.

Safety

Confirm the safety of BBL injection for the correction of volume loss in the IOH area.

3 Determination of Sample Size

The primary effectiveness analysis considers the proportion of subjects with at least 1-point improvement on the MIHAS for both IOHs, as assessed by the blinded evaluator at Week 8 compared to baseline. For this analysis, subjects from TN and TC groups will be pooled into the Treatment Group TRT, and subjects from CDTN and CDTC groups (data before any treatment) will be pooled into the Control Group (CTL).

A two-step hierarchical-testing procedure is foreseen for the primary analysis:

- 1. Treatment Group (TRT) shows a response rate of more than 50%, and
- 2. Treatment Group (TRT) is superior to the Control Group (CTL).

This hierarchical-testing procedure will keep the overall one-sided error rate of $\alpha = 0.025$, and no adjustment for multiplicity is necessary.

Sample-size estimation was based on methods implemented for the binomial and Fisher's exact test. In this context, it should be noted that the use of two-sided 95% Wilson confidence intervals (CI) and Newcombe CIs, instead of binomial and Fisher's exact tests as referenced in the next paragraph, will deliver more efficient results (i.e. smaller CIs). The CI-based methods have the advantage that they can be used for multiple imputation of missing data. Hence, sample size calculations were based on slightly more conservative test procedures, so that the determined power will also suffice for tests based on CIs.

Sample-size estimation for test Step 1 was performed with a one-sided binomial test at an error level of 2.5% to evaluate whether the response rate was significantly larger than 50%. It was aimed to ensure a power of 90%. The binomial test will be conducted on the pooled data (TRT) from both treatment groups (TN and TC). Due to the allocation ratio of 2:2:1:1, the two treatment groups (TN and TC) will be approximately equally represented. Calculations for test Step 2 were performed with a one-sided Fisher's exact test for unequal n's, at an error level of 2.5%, to detect a statistically significant difference between a response rate in Group TRT of 70% compared to 30% in Group CTL. A power of at least 90% was assumed.

Based on data from a pilot study in the same indication (M930121001) showing responder rates of above 80% for observed data and above 70% with missing data treated as no change from baseline (no response), a true responder rate of 70% for this pooled Group TRT sample was assumed. Under these assumptions, a total of 80 subjects are needed to reach a power of at least 94% in test Step 1.

For test Step 2 and maintaining the assumption to have 70% response rate in Group TRT and 30% in Group CTL, a sample size of 80 subjects in Group TRT and 40 subjects in Group CTL reaches a power of at least 98% to demonstrate statistically different response rates between the groups.

To account for up to 20% drop-outs, 150 subjects will be randomized in this study (i.e., 50 subjects into each treatment group [TN and TC] and 25 subjects to each control group [CDTN and CDTC]). The conservative approach for this hierarchical-test procedure has an overall power of above 92%.

If 150 subjects are treated, the sample size is sufficient to observe, with a probability of 80%, at least one AE (adverse event) with actual event probability of 1.1%.

Sample size calculations were performed using nQuery software (Version 8, Statistical Solutions Ltd., 2017).

4 Analysis Sets

In addition to the randomized treatment groups (TN, TC, CDTN and CDTC; see Section 2.1), the following treatment groups will be defined for randomized subjects as follows:

- Treatment group (TRT): All subjects from TN and TC groups;
- Control group (CDTRT): All subjects from CDTN and CDTC;
- CTL: All subjects from CDTN and CDTC groups (only data until first treatment will be considered for analysis.);
- DTN: Subset of subjects within CDTN (only data from first (delayed) treatment onward will be considered for analysis);
- DTC: Subset of subjects within CDTC (only data from first (delayed) treatment onward will be considered for analysis);
- DTRT: All subjects from DTN and DTC (only data from first (delayed) treatment onward will be considered for analysis);
- NED: Subjects that receive treatment with needle-injection technique will be pooled from TN and DTN groups;
- CAN: Subjects that receive treatment with cannula-injection technique will be pooled from TC and DTC groups; and
- TOTT: Subjects that receive treatment at any time during the study (TRT and DTRT) will be pooled from NED and CAN groups.

The following analysis sets will be defined for statistical analysis:

Randomized Population

The randomized population will consist all subjects randomized.

Safety Population (SP)

The SP will consist of all subjects treated.

Intent-to-Treat (ITT) Population

The ITT population will include all randomized subjects of the control group (CTL) and all randomized and treated subjects of the treatment group (TRT).

Per Protocol (PP) Population

The PP population is a subset of subjects in the ITT population without major protocol deviations (PDs). Final determination of what constitutes a major protocol deviation leading to exclusion from PP population will be made in a data review meeting (DRM) prior to database close.

Analyses based on ITT and PP populations and effectiveness analyses based on SP will include subjects as randomized. All other analyses on the SP will include subjects as treated.

5 Endpoints for Analysis

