6.1 Effectiveness Endpoints

6.1.1 Primary Effectiveness Endpoint

The primary effectiveness endpoint is the proportion of responders at Week 8, as assessed live by a blinded evaluator. A responder is defined as a subject with at least 1-point improvement from baseline on MIHAS of both IOHs. For baseline, the MIHAS scores as assessed at Screening will be used. Further details on assessments and visits used for analysis are described in detail in Section 5.1.1.

The primary effectiveness endpoint will be analyzed based on the ITT population. The proportion of responders at Week 8 will be summarized as counts and percentages for the pooled TRT and the pooled CTL groups. For analyses based on multiple imputation as described below, the average number and percentage of responders, over all imputations, will be presented instead. Four hypothesis tests will be performed and will be evaluated in sequential order. The formal hypotheses of each test are given in \square To control for multiplicity, a hierarchical-testing procedure will be performed. Each test will hereby be performed at a one-sided α level of 0.025.

The first two tests for the primary endpoint of treatment versus control will be confirmatory tests as outlined in column and as described in detail in Section 6.1.1.1; if both null hypotheses are rejected, two additional tests will be performed, as confirmative subgroup analyses, to separately investigate the effectiveness of the two injection techniques (i.e., needle and cannula). For the subgroup analyses, the first test is TN vs. CTL and only if this hypothesis can be rejected, the test of TC vs. CTL will be performed. Details on this subgroup analysis are given in Section 6.1.1.3.

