6.1.1.1 Primary analysis

The first hypothesis test of the primary analysis evaluates whether the response rate at Week 8 (Visit 3) in treated subjects is significantly larger than 50%. The analysis will be based on all subjects of the ITT population in the TRT treatment group.

Hypothesis test 1:

 H_{10} : $\pi_{TRT} \leq 50\%$

 H_{11} : $\pi_{TRT} > 50\%$,

where π_{TRT} denotes the responder rate in percent at Week 8 of treated subjects.

The second hypothesis test evaluates whether the response rate in treated subjects at Week 8 (Visit 3) is higher than the response rate in untreated subjects at Week 8 (Visit C1-a). The analysis will be based on all subjects from the ITT population in the TRT and CTL groups.

Hypothesis test 2:

 H_{20} : $\pi_{TRT} \leq \pi_{CTL}$

 H_{21} : $\pi_{TRT} > \pi_{CTL}$,

where π_{TRT} and π_{CTL} denote the responder rates in percent at Week 8 of the treated and untreated subjects, respectively.

Both hypotheses will be tested using the lower limits of the 95% CIs (two-sided), based on Wilson scores. The lower limit of the 95% Wilson CI for the responder rate in the TRT group must exceed the margin of 50% responder rate to reject Hypothesis 1 (H_{10}). The lower limit of the 95% Newcombe CI for the difference between the responder rates in the TRT and the CTL groups (TRT-CTL) must be greater than zero to reject Hypothesis 2 (H_{20}).

Using the Wilson and Newcombe CIs in these tests will allow for imputation of missing values of the primary effectiveness endpoint with a multiple-imputation approach. This procedure will replace missing MIHAS values at Week 8 for the ITT population.

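### The 0.025 one-sided error rate is a nominal level: with complete data the Wilson rule for H1 has exact size 2.84% at n = 100 and 2.83% at n = 80

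*SAP*

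**What the plan says.** SAP section 3 (Determination of Sample Size) sets out a two-step hierarchy. In Step 1, "Treatment Group (TRT) shows a response rate of more than 50%, and" in Step 2, TRT must be superior to CTL. It then says: "This hierarchical-testing procedure will keep the overall one-sided error rate of" 0.025, and concludes that multiplicity needs no adjustment. Protocol 13.2 makes the same statement. SAP 6.1.1 adds: "Each test will hereby be performed at a one-sided" level of 0.025.

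The sizing and the analysis use different tests:

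- **Sizing (SAP section 3).** "Sample-size estimation for test Step 1 was performed with a one-sided binomial test at an error level of 2.5"%. Fisher's exact test was used for Step 2.
- **Decision (SAP 6.1.1.1).** "The lower limit of the 95% Wilson CI for the responder rate in the TRT group must exceed the margin of 50% responder rate" for H1 to be rejected. H2 is rejected if the lower Newcombe limit for TRT minus CTL is above zero.

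Section 3 acknowledges the switch. It describes the exact tests as slightly more conservative, and it uses that to argue that the power computed for them carries over to the interval rules. It does not say what the switch does to the type I error. The same section also says, in the future tense, that the pooled TRT data will be tested with the binomial test, which is not the rule in 6.1.1.1.

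**The concern.** An exact binomial test cannot exceed its stated level. A Wilson limit is the inversion of a score test based on a normal approximation, so its level is 2.5% on average over sample sizes but not at each one. If an interval rule is more efficient than an exact test because it rejects at a lower count, that gain is paid for in type I error.

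H1 comes first in the hierarchy. When the true TRT rate is 50% and TRT truly exceeds CTL, the only false rejection possible in the two primary steps is that of H1, so the size of its rule is their error rate. The plan therefore states as a property of the procedure something that the chosen rule has only nominally. At stake is the accuracy of a stated error rate in a pivotal study, and a decision that differs between the two Step 1 tests if the count falls exactly on the boundary.

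**Working it through.** **Inputs.** Null rate for H1: 50%. Level: one-sided 0.025. Assumed rates: TRT 70% ("a true responder rate of 70% for this pooled Group TRT sample was assumed") and CTL 30%. Evaluable n: 80 and 40. Randomized n: 2 × 50 = 100 TRT and 2 × 25 = 50 CTL. All are from SAP section 3.

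**1. The plan's own figures reproduce.**

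- Step 1, exact binomial, n = 80: reject at 50 or more responders. P(X ≥ 50 | 0.5) = 1.65%. P(X ≥ 50 | 0.7) = 94.1%. The SAP says "a total of 80 subjects are needed to reach a power of at least 94% in test Step 1".
- Step 2, one-sided Fisher, 80 versus 40, full enumeration: 98.4% (stated: at least 98%).
- Overall: 0.9413 × 0.9837 = 92.6% (stated: above 92%).
- Drop-out: 120 / 0.8 = 150.

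**2. Cut-off of the Wilson rule, complete data.** The lower limit is

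L = [p + z²/(2n) − z·√(p(1−p)/n + z²/(4n²))] / (1 + z²/n), with z = 1.96.

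For 60/100: L = (0.6192 − 1.96 × 0.04996) / 1.0384 = 0.5020, so H1 is rejected. For 59/100: L = 0.4920, not rejected. At n = 80, 49 responders give 0.5029 and 48 give 0.4905.

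**3. Exact size and power.**

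| n | Rule | Reject at | Size at 50% | Power at 70% |
|---|---|---|---|---|
| 80 | exact binomial | 50 | 1.65% | 94.1% |
| 80 | Wilson | 49 | 2.83% | 96.4% |
| 100 | exact binomial | 61 | 1.76% | 97.9% |
| 100 | Wilson | 60 | 2.84% | 98.8% |

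**4. Dependence on n.** Over n = 80 to 100 the Wilson size runs from 1.98% (n = 95) to 3.15% (n = 84), with a mean of 2.53%. It is above 2.5% at 11 of the 21 values, and one of those is 2.51% (n = 85). At the other 10 values the Wilson and exact cut-offs coincide; for example, both are 60 at n = 99, with size 2.19%.

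**5. Does Step 2 absorb the excess?** Enumerating both binomials at 100 versus 50 with TRT at 50%, the probability of rejecting both H1 and H2 is 2.84% for a control rate of 5% to 20% and 2.80% at 30%. It does not.

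**6. Error for H2 when the two rates are equal.** H2 counts only if H1 has been rejected. At 100 versus 50 the probability of rejecting both is 0.68% at a common rate of 50%, 1.90% at 55%, 2.57% at 60% and 2.74% at 70%, with a maximum of about 2.87% near 83.5%. The Newcombe rule alone gives 2.82% at 50%, but that is not the error of the two-step procedure.

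**7. Missing data.** The SAP applies a multiple-imputation version of the Wilson limit, with a t quantile and a between-imputation term. A simplified simulation of that formula (assumptions: one binary outcome imputed, missing at random, n = 100, 100 imputations, 200,000 runs) gave 2.73%, 2.39%, 2.29% and 2.62% with 2, 5, 10 and 20 subjects missing. A similar 40,000-run simulation gave about 2.75%, 2.2%, 2.2% and 2.8%. Neither uses the SAP's model, which imputes MIHAS scores separately for each IOH. For TRT that model uses baseline, Week 4, site and touch-up.

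**The case against.** The sentence on the error rate ends by saying that no multiplicity adjustment is needed. Read in that context, it is about the ordering of the tests, and on that it is right. Calling a rule based on a 95% score interval one-sided 0.025 is ordinary nominal usage, and no figure in the plan is miscalculated. All of this stands.

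It also stands that n = 100 is a fragile reference point. It is the number randomized to TRT, while the ITT population counts only TRT subjects who were treated. One untreated subject gives n = 99 and a size of 2.19%.

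A reader might infer more than the documents support:

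- **That the Wilson rule is systematically anti-conservative.** It is not. The mean size of 2.53% and the 11-to-10 split over n = 80 to 100 show binomial discreteness around the nominal level.
- **That the hierarchy fails to control multiplicity.** It does not fail. The excess belongs to the individual interval rules.
- **That H2 is inflated wherever both rates exceed 50%.** With Step 1 in front, the excess begins only near 60%, while the planned control rate is 30%.
- **That the rule actually applied has size 2.84%.** That figure is for complete data. The simplified simulations fall on both sides of 2.5%.

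What the objection does not remove is that both documents give 0.025 without the word nominal, and that neither, in the text available, reports the size of the rule that replaced the exact test.

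**Conclusion.** The point holds as a matter of exact statement. With complete data, the H1 rule has size 2.84% at n = 100 and 2.83% at n = 80, the two TRT sizes the plan uses, against a stated 0.025. The excess is about 0.34 percentage points, or one responder at the cut-off, and Step 2 does not remove it. For H2 under equal rates at 100 versus 50, the excess is at most about 0.37 points (2.87% − 2.50%) and arises only at rates of about 60% or more.

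These figures assume independent subjects, complete Week 8 data and the stated group sizes. The size under the SAP's imputation model is unknown.

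The practical weight is low. At n = 100 the two Step 1 tests differ only at exactly 60 responders, while the assumed 70% rate would give 70. Nothing here calls the design, the sample size or the choice of Wilson and Newcombe limits into question.

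**What to change.** 1. In SAP section 3 and Protocol 13.2, describe 0.025 as the nominal one-sided level. Keep the statement that the fixed sequence needs no multiplicity adjustment.
2. Add one sentence with the exact complete-data size of the H1 rule: about 2.8% at n = 80 and n = 100, and up to 3.15% at sample sizes in between. Say that the size under multiple imputation has not been evaluated, unless it is simulated under the planned MIHAS model.
3. In SAP section 3, and in the parallel sentence of Protocol 13.2, make clear that the binomial test was used for sizing only and that the Wilson limit in SAP 6.1.1.1 decides H1. As written, the two give opposite answers at 60/100.

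An exact binomial test on observed cases should not be added as a further condition for H1. It would make confirmatory success depend on a completers' analysis, against the plan's reason for choosing interval methods that work with multiple imputation. It would also leave H2 as it is.

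The cost is a few sentences and a slightly less favourable stated error rate. Sample size, power statements and study conduct do not change.

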5.1 Effectiveness Endpoints

5.1.1 Primary Effectiveness Endpoint

Proportion of responders at Week 8 on the MIHAS, as assessed live by a blinded evaluator.

Note: Responder is defined as a subject with at least 1-point improvement from baseline on MIHAS of both IOHs.

Note: For subjects randomized to treatment, if no touch-up is performed, the primary effectiveness MIHAS assessment will occur 8 weeks post baseline injection. If a touch-up is performed, the primary effectiveness MIHAS assessment will be completed 8 weeks post touch-up. For subjects randomized to control/delayed-treatment, the primary effectiveness assessment will occur 8 weeks from the screening visit. I.e. MIHAS data from Visit 3 will be used for subjects randomized to treatment and MIHAS data from Visit C1-a will be used for subjects randomized to control/delayed-treatment.

5.1.2 Secondary Effectiveness Endpoints

Note: For all secondary endpoints, Week 8 corresponds to the time from last injection (either baseline or touch-up injection) for subjects randomized to treatment only (TN and TC groups). I.e. data from Visit 3 will be used.

- GAIS score at Week 8, as assessed by the treating investigator.
- GAIS score at Week 8, as assessed by the subject.
- FACE-QTM Satisfaction with Eyes scores and changes from baseline to Week 8, as assessed by the subject.

Note: FACE-Q evaluates both eyes concurrently.

[figure not shown]
5.2 Safety Endpoints

5.2.1 Primary Safety Endpoints

Not applicable.

5.2.2 Secondary Safety Endpoints

- Incidence of treatment-emergent adverse events (TEAEs) related to BBL.
- Incidence of treatment-emergent serious adverse events (TESAEs) related to BBL.

6 Statistical Analysis Methods

Metric statistics will be number of values analyzed (n), mean, standard deviation, median, quartiles, minimum, and maximum. If available, number of missing (Nmiss) or number of imputed values will be presented. Mean, quartiles, and median will be reported to one decimal place more than the data were collected, for the standard deviation two decimal places more will be displayed; for derived data, the number of decimal places will explicitly be given in the sections below.

Frequency tables for qualitative endpoints will be absolute and percent frequencies (n, %). In case of missing values, frequency tables will include the number of missing values. Percentages will be calculated using the denominator of all subjects in a specified population or treatment group. For visit-based data and if not otherwise specified, percentages will be calculated using the number of subjects with non-missing data at the corresponding visit as denominator (observed cases). The denominator will be specified in a footnote to the tables for clarification if not otherwise obvious. Percentages will be reported to one decimal place.

If not otherwise specified, statistical tests will be conducted one-sided at type I error rate 2.5%. P-values will be reported to four decimal places (e.g., p=0.0375). P-values below 0.0001 will be presented as '<0.0001'. CIs will be two-sided 95% CIs.

The following definition of treatment cycles will be used in several analyses.

For subjects of treatment groups TN and TC who receive retreatment, Cycle 1 is the period from initial injection to the retreatment injection (at 48 weeks after the last injection [either initial or touch-up injection]) and Cycle 2 is the period from retreatment injection until study end (i.e. date of last contact). Analyses for Cycle 2 will therefore present results at visit V8 as 8 weeks post-injection in Cycle 2, rather than as 56 weeks post last injection in Cycle 1. Similarly, results at visit V9 will be presented as 24 weeks post-injection in Cycle 2.

For subjects of treatment groups TN and TC who do not receive retreatment and for subjects of treatment groups DTN and DTC, Cycle 1 is defined as the period from initial injection until study end. Results at visit V8 and V9 for TN and TC subjects will be presented as 56 and 72 weeks post last injection (in Cycle 1), respectively.

Subjects who never received treatment do not have a cycle 1 or cycle 2.

Section 6.4.1 describes methods for handling of data collected at the end of study visit (either visit V9 for subjects in TRT or visit C7 for subjects in CDTRT) among subjects prematurely discontinuing the study.

For the primary and secondary effectiveness analyses, if not stated otherwise, "Week 8" refers to visit V3 (8 weeks post last injection in Cycle 1) for subjects in TRT, TN, and TC and visit C1-a (8 weeks post screening) for subjects in CTL.

All data will be listed. If not stated otherwise, listings will be presented based on all subjects randomized.

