	All eligible subjects will be randomized to 4 groups using a 2:2:1:1 ratio as follows: BBL with needle (TN), BBL with cannula (TC), control/delayed treatment BBL with needle (CDTN), and control/delayed treatment BBL with cannula (CDTC).
Introduction, Study Design Overview, and Methodology	Subjects randomized to treatment will receive a BBL injection in both IOHs and will be assessed at Week 4 for a touch-up in one or both IOHs. These subjects will also be eligible for a retreatment at 48 weeks post last injection (i.e., baseline injection or touch-up, if applicable) and then be followed for an additional 24 weeks, for a total study duration of 72 weeks if no touch-up is performed and 76 weeks if a touch-up is performed.
	Subjects randomized to the control/delayed-treatment group will remain untreated for 8 weeks. After all applicable effectiveness endpoint assessments have been completed, the control/delayed-treatment subjects will receive BBL injections and will be assessed 4 weeks after their initial injection for a touch-up in one or both IOHs. These subjects will be followed for 48 weeks post last injection (i.e., baseline injection or touch-up, if applicable) and will not be offered retreatment.
Number of Study Subjects	A total 150 subjects will be randomized.
	Select inclusion criteria are as follows:
	Subject is a candidate for bilateral IOH treatment.
	• Subject has symmetrical right and left IOHs with the same MIHAS score of 2 or 3 (moderate or severe), as assessed live by a blinded evaluator.
	• Female or male ≥ 22 and ≤ 65 years old.
Main Inclusion/ Exclusion Criteria	Select exclusion criteria are as follows:
	• Prior lower-eyelid surgery, including orbital or midface surgery, or a permanent implant or graft in the midfacial region that could interfere with effectiveness assessments.
	• Previous treatment with fat injections or permanent and/or semi- permanent dermal fillers in the midfacial region.
	• Previous lower-eyelid and/or malar-region treatments with any dermal fillers (e.g., collagen, hyaluronic acid (HA), calcium hydroxyapatite, poly L-lactic acid (PLLA)) within the past 24 months.

	Tendency to accumulate fluid in the lower eyelids, has developed festoons, or has large and/or herniating infraorbital fat pads.
Duration of Treatment	Subjects will have a screening period of up to 10 days and participate for a maximum duration of 76 weeks (\pm 14 days).

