Subjects who achieve at least 1-point improvement on the MIHAS 4 weeks post treatment when compared to baseline may have a touch-up injection in one or both IOH(s) to achieve optimal correction, at the discretion of the treating investigator and the subject.

Subjects randomized to treatment (TN or TC) at Day 1, will have the option for retreatment, upon agreement between the subject and the treating investigator, at 48 weeks post last injection (i.e., baseline injection or touch-up, if applicable) and will then be followed for an additional 24 weeks, for a total study duration of up to 76 weeks (72 weeks if no touch-up was performed).

Subjects randomized to the control/delayed-treatment group (CDTN or CDTC) will remain untreated until Week 8. After all applicable effectiveness endpoint assessments have been completed at their Week 8 visit, control subjects will receive BBL IOH injections (i.e., delayed treatment) and will be followed for 48 weeks. Subjects who do not achieve optimal aesthetic correction or at least 1-point improvement on the MIHAS as assessed by the blinded evaluator 4 weeks post treatment compared to the delayed-treatment baseline (Week 8), may have a touch-up injection in one or both IOH(s). If a touch-up is necessary, it will only be administered if there are no medical contraindications or existing AEs of concern, as determined by the treating investigator. The treating investigator will be responsible for reviewing whether the threshold for optimal aesthetic correction or at least 1-point MIHAS improvement is met, as assessed by the blinded evaluator, since the blinded evaluator will not have access to the subject's study records.

Subjects from the control/delayed treatment group who achieve at least 1-point improvement on the MIHAS 4 weeks post treatment when compared to the delayed-treatment baseline (Week 8) may have a touch-up injection in one or both IOH(s) to achieve optimal correction, at the discretion of the treating investigator and the subject.

Control/delayed-treatment subjects will not be offered retreatment.

Any time a subject is treated (i.e., initial injection, touch-up, and/or retreatment), he/she will have a 72-hour post-treatment phone call to evaluate safety. If a subject reports a safety concern during any phone call, an unscheduled visit may be necessary.

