6.2 Safety Endpoints

All safety endpoints will be summarized for observed values in the SP by treatment group (TRT and DTRT) and overall (TOTT) and by injection technique (needle/cannula) (groups TN, DTN and NED as well as TC, DTC and CAN), if not otherwise stated. Analyses by treatment cycle will be based on the subset of subjects in the SP with treatment in the respective cycle.

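### By-cycle TEAE percentages rest on unequal follow-up (24 weeks in Cycle 2, 48 to 76 weeks in Cycle 1), so the tables can mislead about the safety of repeat treatment

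*SAP*

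**What the plan says.** **Cycle definitions (SAP Section 6).**
- Retreated TN and TC subjects: "Cycle 1 is the period from initial injection to the retreatment injection (at 48 weeks after the last injection", counted from the initial or touch-up injection, whichever came last. After that, "Cycle 2 is the period from retreatment injection until study end (i.e. date of last contact". For effectiveness, "results at visit V9 will be presented as 24 weeks post-injection in Cycle 2".
- TN and TC subjects not retreated: Cycle 1 runs to study end. "Results at visit V8 and V9 for TN and TC subjects will be presented as 56 and 72 weeks post last injection", still in Cycle 1.
- Delayed treatment: for "subjects of treatment groups DTN and DTC, Cycle 1 is defined as the period from initial injection until study end". The Protocol synopsis fixes that end: "These subjects will be followed for 48 weeks post last injection (i.e., baseline injection or touch-up, if applicable) and will not be offered retreatment".

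**Counting rule (SAP 6.2 and 6.2.1; Protocol 13.4.2).** A TEAE goes to a cycle by its onset date, with no fixed window after injection. Tables give subjects affected and event counts, per cycle and overall. The denominator is a number of subjects: "Analyses by treatment cycle will be based on the subset of subjects in the SP with treatment in the respective cycle".

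**What is not visible.** The readable text gives no subject-time denominator, no exposure-adjusted rate and no common post-injection window for TEAEs. The Extent of exposure paragraph covers treatments, volume and technique, not length of follow-up. Parts of the safety text are redacted, so an adjustment there cannot be ruled out.

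**Related displays already planned.** TEAE tables are split by touch-up (Cycle 1 only). Related TEAEs starting more than 28 days after the latest injection are flagged in a listing. Common treatment responses (CTRs) are collected by diary for 28 days after each injection and summarised per injection (Protocol 13.4.2).

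**The concern.** Safety is one of the two study objectives, and incidence of related TEAEs is a secondary endpoint. Protocol 8.2 gives safety information on repeat treatment as one reason for offering retreatment. The by-cycle TEAE tables are where a reader will look for it.

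A percentage of subjects with at least one event rises with time at risk. If Cycle 1 is two to three times as long as Cycle 2, Cycle 2 can look safer when nothing differs. Cycle 1 also mixes lengths within one column: TN/TC subjects who decline retreatment contribute 24 more weeks than those who accept. The pooled Cycle 1 figure therefore depends partly on uptake of an optional procedure.

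**Working it through.** **1. The plan's own figures.** SAP 2.1 gives TN/TC participation "for a total study duration of up to 76 weeks (72 weeks if no touch-up was performed"). Check: 48 + 24 = 72 weeks; with the Week 4 touch-up, 4 + 48 + 24 = 76 weeks. The visit-window tables in SAP 6.4.1 agree: target days 337, 505 and 169 are (337 − 1)/7 = 48, (505 − 1)/7 = 72 and (169 − 1)/7 = 24 weeks.

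The only numerical safety statement is an 80% chance of seeing at least one AE of probability 1.1% in 150 subjects. It reproduces: 1 − 0.989^150 = 0.810. It attaches no time period to the event probability.

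**2. Nominal length of each cycle (weeks).**

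| Group | Cycle 1, no touch-up | Cycle 1, touch-up | Cycle 2 |
|---|---|---|---|
| TN/TC retreated | 48 | 52 | 24 |
| TN/TC not retreated | 72 | 76 | none |
| DTN/DTC | 48 | 52 | none |

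Cycle 1 is 48/24 = 2.0 to 76/24 = 3.2 times as long as Cycle 2.

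**3. Same constant rate in both cycles.** The documents give no TEAE rate, so weekly rates λ from 0.002 to 0.02 are assumed. Expected percentage with at least one event = 100 × (1 − exp(−λ × weeks)).

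| λ per week | 24 wk (Cycle 2) | 48 wk | 52 wk | 72 wk | 76 wk | Cycle 1 / Cycle 2 |
|---|---|---|---|---|---|---|
| 0.002 | 4.7 | 9.2 | 9.9 | 13.4 | 14.1 | 1.95 to 3.01 |
| 0.005 | 11.3 | 21.3 | 22.9 | 30.2 | 31.6 | 1.89 to 2.80 |
| 0.01 | 21.3 | 38.1 | 40.5 | 51.3 | 53.2 | 1.79 to 2.49 |
| 0.02 | 38.1 | 61.7 | 64.7 | 76.3 | 78.1 | 1.62 to 2.05 |

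**4. Effect of retreatment uptake.** Take the planned 100 TRT and 50 delayed-treatment subjects, λ = 0.005 and a 30% touch-up share (assumed). With half of TRT retreated:
- Retreated TRT, and DTRT: 0.7 × 21.3 + 0.3 × 22.9 = 21.8%.
- Non-retreated TRT: 0.7 × 30.2 + 0.3 × 31.6 = 30.6%.
- TRT Cycle 1: the average of the two, 26.2%. All treated subjects (TOTT): (100 × 26.2 + 50 × 21.8)/150, which is 24.8% before rounding of inputs, against 11.3% in Cycle 2.

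If 30% or 80% are retreated instead, TRT Cycle 1 becomes 28.0% or 23.6%, with the same underlying rate.

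**5. Events only shortly after an injection.** Let each injection session carry risk q (assumed independent and equal), and let t be the touch-up share. Cycle 2 shows q. Cycle 1 shows (1 − t) × q + t × (1 − (1 − q)²).

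| q | Cycle 2 | Cycle 1, t = 0 | t = 30% | t = 60% |
|---|---|---|---|---|
| 10% | 10.0 | 10.0 | 12.7 | 15.4 |
| 30% | 30.0 | 30.0 | 36.3 | 42.6 |

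Window length adds nothing here. The gap is entirely the second session counted in Cycle 1.

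**6. Equal windows.** Over 24 weeks after the first injection of each cycle, equal constant rates give equal percentages: 4.7, 11.3, 21.3 and 38.1 for the four rates in step 3.

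**The case against.** The strongest reply concerns the shape of the hazard. The secondary safety endpoints are events related to the device, and Protocol 6.2 describes the main injection-site responses as starting soon after treatment and resolving within 14 days. For those, step 5 applies rather than step 3. CTRs also have an equal 28-day display for each injection, which compares first and repeat treatment fairly for expected acute responses. No test between cycles is planned. All of this stands, and it limits the point to a risk of misreading descriptive tables, mainly for all-cause and late-onset TEAEs.

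It does not remove the point. The CTR display covers predefined responses, not TEAEs in general. The delayed-onset flag is in a listing and yields no incidence over equal time. The touch-up split leaves Cycle 1 at 48 or 72 weeks (52 or 76 with touch-up) against 24.

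A reader might infer four stronger things that the documents do not support:
- That Cycle 2 will read about half as high for TEAEs generally. This needs a roughly constant rate.
- That every subject who is not retreated has a longer Cycle 1. This holds for TN/TC only; DTN/DTC subjects are never retreated, yet have 48 to 52 weeks.
- That no column has a common length. Cycle 2 is nominally 24 weeks throughout.
- That the two cycles hold unrelated subjects. Cycle 2 subjects are a subset of Cycle 1 subjects, selected because retreatment is optional and is barred after treatment-related visual abnormalities (Protocol 11.2.2.2.1).

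**Conclusion.** The point holds as a cheap reporting improvement. The unequal lengths follow directly from the documents. Under a constant rate equal in both cycles, the Cycle 1 percentage is about 1.6 to 3.0 times the Cycle 2 percentage with no true difference, and pooled Cycle 1 moves with retreatment uptake. For acute events the gap comes only from touch-ups and is smaller: 12.7% or 15.4% against 10.0% at an assumed 10% risk per session.

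The rates, per-session risks, touch-up shares and retreatment shares are all assumptions, and the lengths are nominal, without early withdrawal. As planned, the visible TEAE tables cannot show whether a second treatment carries more, equal or less risk. They do not bias any planned test.

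**What to change.** Keep the planned by-cycle tables and add the following to SAP 6.2.1:

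1. Subject-time and exposure-adjusted TEAE rates by cycle. Read these beside the percentages, not instead of them: for events clustered after injection, the same risk spread over 48 rather than 24 weeks would halve the rate and favour Cycle 1.
2. A separate display of events in non-retreated TN/TC subjects after Week 48 post last injection. Simply closing Cycle 1 at that point would not be enough, since 48 to 52 weeks would still stand against 24.
3. A table of related and of all TEAEs in the first 24 weeks after the initial injection against the 24 weeks after retreatment, in retreated subjects only. Split it by touch-up, because the Week 4 touch-up falls inside the first window.
4. A footnote that retreated subjects are a selected subset, so early related events may be under-represented in their Cycle 1 window. This could make Cycle 2 look relatively worse.

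Protocol 13.4.2 carries the same cycle assignment, so its wording and the SAP's should be aligned. The onset, injection and last-contact dates are already used in the plan, so no new data are needed, and endpoints, tests and conduct are unchanged. The cost is SAP wording and one or two extra tables.
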